7.4. Dose-Limiting Toxicity

An event, occurring within the first 28 days (*i.e.*, Day 0 to Day 28) that meets at least one of the following conditions:

- Any local reaction that requires operative intervention and is felt to be attributable to study drug
- Any local reaction that has life-threatening consequences requiring urgent intervention or results in death and is felt to be attributable to study drug
- Any Grade 3 or higher non-hematologic adverse event that is at least possibly related to study drug and lasts ≥ 3 days
- Nausea and vomiting will not be considered a DLT unless at least Grade 3 or 4 and refractory to antiemetics (*i.e.*, defined as symptoms unrelieved by maximal medical support as directed by the PI (per institutional guidelines) in consultation with the medical monitor).
- Grade 3 or higher thrombocytopenia ($< 50,000/\text{mm}^3$) at least possibly related to study drug

- Any Grade 4 or higher hematologic toxicity (except thrombocytopenia) that is at least possibly related to study drug and lasts ≥ 5 days

Dose escalation may be stopped by the Medical Monitor before a DLT is observed, but where the observed toxicities indicate the strong likelihood of unacceptable toxicity at higher doses.

Note: Diagnostic brain tumor biopsy is not considered a DLT. Seizures, headaches, and cerebral or pontine edema are commonly observed in this population and will be recorded according to the grade of toxicity but will not be considered a DLT unless a relationship to study drug is deemed to be the main contributory factor. Transient neurological changes are expected in Arm 2 and will not be considered a DLT unless they last > 10 days.

Expansion cohorts will be allowed in Arm 2 if deemed appropriate by the SRC. If an expansion cohort is implemented, the veledimex dose may be delayed or reduced for individual subjects in the event of toxicity. If $\geq 33\%$ of subjects in the expansion cohort experience DLTs, using the definition in the dose-escalation phase, additional subjects may be enrolled at the next lower dose tested in the dose-escalation phase or at an intermediate dose, as recommended by the SRC. All DLTs should be reported to the Sponsor within 24 hours of Investigator/site awareness.

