Note: Diagnostic brain tumor biopsy is not considered a DLT. Seizures, headaches, fatigue and cerebral or pontine edema are commonly observed in this population and will be recorded according to the grade of toxicity but will not be considered a DLT unless a relationship to study drug is deemed to be the main contributory factor. Transient neurological changes are expected in Arm 2 and will not be considered a DLT unless they last > 10 days.

Expansion cohorts will be allowed in Arm 2 if deemed appropriate by the SRC. If an expansion cohort is implemented, the veledimex dose may be delayed or reduced for individual subjects in the event of toxicity. If $\geq 33\%$ of subjects in the expansion cohort experience DLTs, using the definition in the dose-escalation phase, additional subjects may be enrolled at the next lower dose tested in the dose-escalation phase or at an intermediate dose, as recommended by the SRC. All DLTs must be reported to the Sponsor within 24 hours of Investigator/site awareness.

Definition of Recommended Phase II Pediatric Dose:

The recommended Phase II pediatric veledimex dose will be determined from the Evaluable Safety Population (ESP), as defined below. The recommended Phase II pediatric dose is defined as the dose level below the dose in which $\geq 33\%$ of subjects in the same cohort experience DLTs. If two DLTs occur in the same cohort, subject dosing will stop in the cohort experiencing the DLTs.

Safety Evaluation:

Safety will be evaluated in the Overall Safety Population (OSP) and the Evaluable Safety Population (ESP), as defined below, using National Cancer Institute (NCI) Common Terminology Criteria for Adverse Events (CTCAE) v5.0.

In the DLT evaluation period (Day 0 to Day 28), if any subject experiences a local reaction that requires operative intervention and is felt to be attributable to study drug(s); any local reaction that has life-threatening consequences requiring urgent intervention or results in death and is felt to be attributable to study drug; or any Grade 4 hematologic toxicity, except thrombocytopenia, that is at least possibly related to study drug and lasts ≥ 5 days, enrollment of new subjects will be paused pending review by the SRC.

Safety assessments will be based on medical review of adverse event reports and the results of vital signs, physical and neurologic examinations, electrocardiograms (ECGs), clinical laboratory tests, and

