7.8. Severity Grading and Management of Local Reactions

Injection of agents into tissue carries a potential risk of local reactions that may be characterized as intense immunologic reaction at or near the injection site. Local reactions will be graded according to the NCI CTCAE v5.0 criteria. Study stopping rules will not apply to a specific event if it is clearly unrelated to study drug administration.

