7.10. Study Stopping Rules

In the DLT evaluation period (Day 0 to Day 28), if any subject experiences a local reaction that requires operative intervention and is felt to be attributable to study drug; any local reaction that has life-threatening consequences requiring urgent intervention or results in death and is felt to be attributable to study drug; or any Grade 4 hematologic toxicity, except thrombocytopenia, that is at least possibly related to study drug and lasts \geq 5 days, enrollment of new subjects will be paused pending review by the SRC.

In the event that there are other subjects actively being dosed in the cohort, the treating site's Principal Investigator (PI) and the Medical Monitor will discuss the relationship to study drug and determine whether or not to convene an urgent SRC meeting to make a decision to continue active dosing in ongoing subjects.

The SRC will make a decision to the enrollment of additional subjects at the relevant veledimex dose level, to expand the current dose level cohort, to de-escalate veledimex dosing at the relevant dose level, or to amend the protocol prior to enrollment of additional subjects, or to discontinue enrollment in the study. In the event that a decision is made to de-escalate dosing, the SRC will evaluate the appropriateness of dosing at a previously evaluated lower dose or exploring an intermediate dose level.

For any subject death within 30 days of study therapy, enrollment will be held pending review of the event by the SRC. Active dosing in ongoing subjects will continue at the discretion of the treating site's PI and the Medical Monitor pending the SRC review.

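### The DLT Note exempts cerebral or pontine edema without any severity limit, so an operative, life-threatening or fatal edema at the injected site that is attributed to study drug can go uncounted

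*Protocol*

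**What the plan says.** Protocol 7.4 lists the conditions that make an event in Days 0 to 28 a DLT; meeting any one is enough. The first two concern local reactions. One covers a reaction that leads to an operation and is attributed to the study drug. The other covers the gravest outcomes, under the same attribution test: "Any local reaction that has life-threatening consequences requiring urgent intervention or results in death and is felt to be attributable to study drug".

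The Note that follows the list takes up seizures, headaches and cerebral or pontine edema. Their grade is recorded, but such an event "will not be considered a DLT unless a relationship to study drug is deemed to be the main contributory factor". The exemption is repeated in three places, each without a severity limit:

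- the synopsis, whose Note adds fatigue: "Seizures, headaches, fatigue and cerebral or pontine edema are commonly observed in this population"
- Protocol 7.6, also with fatigue
- SAP 4.3, which requires the main-cause relationship to be documented where the protocol says deemed.

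Two other sections deal with local reactions. Section 7.8 says that they "may be characterized as intense immunologic reaction at or near the injection site", and also that "Study stopping rules will not apply to a specific event if it is clearly unrelated to study drug administration". Section 7.10 lists "any local reaction that has life-threatening consequences requiring urgent intervention or results in death and is felt to be attributable to study drug" among its triggers, together with operative local reactions attributed to drug. When one occurs, "enrollment of new subjects will be paused pending review by the SRC". Section 7.10 has no edema exemption.

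**The concern.** The list and the Note apply different causality tests to what can be the same event. The local-reaction criteria ask whether the event is attributed to study drug. The Note asks whether study drug is the main cause. An edema at the injected site could be judged attributable to drug while tumor, recent radiotherapy or surgery is judged the larger contributor. In Arm 2 such competing explanations are to be expected, because subjects have DIPG and are injected 2 to 10 weeks after focal radiotherapy.

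That event would pause enrollment under 7.10 and could still score zero DLTs. The DLT count feeds four things: the 3+3 decisions in Table 5 (7.3), the recommended Phase II dose (7.5), the DLT part of the primary endpoint (16.3.1) and, because 7.4 reuses the same definition, the 33% rule in the expansion cohort. Section 7.8 describes local reactions as immunologic reactions around the injection site, and edema there is a natural form of that. The most severe cases of a toxicity the design should be watching for could therefore be left out of the dose decision.

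**Working it through.** The plan states no figure on this point, so there is none to reproduce. The check compares the texts and then traces what one uncounted event does to each rule.

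**Texts side by side, for one event: edema at the injected site that is operative, life-threatening or fatal**

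| Provision | Causality test | Severity limit on any exemption | Result if attributed to drug but mainly due to something else |
|---|---|---|---|
| 7.4, first two criteria | Attributed to study drug | No exemption | DLT |
| 7.4 Note (also synopsis, 7.6, SAP 4.3) | Study drug is the main cause | None | Not a DLT |
| 7.10 | Attributed to study drug | No edema exemption | Enrollment pauses |
| 7.8 | Released from the stopping rules only if clearly unrelated | No edema exemption | Stopping rules apply |

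The causality scale in 14.5 classes an event as related from the possibly-related level upward and allows an alternative etiology at that level. It has no main-cause category. It also does not define the attribution wording, so it does not settle how far apart the two tests are.

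**Effect of one event on the decision rules** (Table 5: 0 of 3 or at most 1 of 6 passes, 1 of 3 adds at least three subjects, 2 or more stops escalation; the cut-off in 7.4 and 7.5 is at least 33%)

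| Situation | Exempt | Counted |
|---|---|---|
| One such event in the first three subjects, no other DLT | 0/3 = 0%: may expand or escalate | 1/3 = 33.3%: enroll at least three more |
| One counted DLT in the first three, one such event in the next three | 1/6 = 16.7%: passes | 2/6 = 33.3%: stops and meets the cut-off |
| 30-subject expansion, nine other DLTs, one such event | 9/30 = 30.0%: below the cut-off | 10/30 = 33.3%: meets the cut-off |

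**Probability that a cohort passes the 3+3 rule.** Let p be the per-subject probability of a counted DLT. A cohort passes with 0 of 3, or with 1 of 3 followed by 0 of 3:

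P(pass) = (1 − p)³ + 3p(1 − p)² × (1 − p)³ = (1 − p)³ + 3p(1 − p)⁵

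Assumed rates: other DLTs occur in 10% of subjects, and the edema in question in a further 2%, 5% or 10%.

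- Exempt, p = 0.10: 0.729 + 0.30 × 0.5905 = 0.906
- Counted, p = 0.12: 0.6815 + 0.36 × 0.5277 = 0.871
- Counted, p = 0.15: 0.6141 + 0.45 × 0.4437 = 0.814
- Counted, p = 0.20: 0.512 + 0.60 × 0.3277 = 0.709

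The exemption thus raises the pass probability by 3.5, 9.2 or 19.7 percentage points in the three cases. The last case makes a narrow class of event as common as all other DLTs combined, so it is an upper end and not an expectation.

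**The case against.** The strongest reply is that no conflict exists. An event is a DLT if it meets any one listed condition, the Note is about symptoms common in this population, and 7.8 treats local reactions as a class of their own. On that reading a fatal injection-site reaction attributed to drug falls under the first two criteria whatever the Note says. The reading is possible, but the text does not state it. If meeting any criterion always prevailed, the Note would exempt nothing. To have any effect it must override at least one criterion, and the documents never confine it to the Grade 3 non-hematologic line.

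Second, the overlap may be empty. The local-reaction criteria use different wording from the possibly-related test applied elsewhere in 7.4, and a site may take attributed to mean mainly caused by. The two tests then coincide. This stands as a limit on size. Other severe local reactions, such as hemorrhage or necrosis, remain DLTs in any case.

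Third, the event will not pass unreviewed:

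- 7.10 pauses enrollment and also holds it after any death within 30 days of study therapy.
- Each escalation subject is observed for 28 days before the next is enrolled.
- Table 6 holds study drug for such local reactions.
- The Investigator and Medical Monitor confer daily during dosing.
- The Medical Monitor may stop escalation before any DLT, and the SRC may de-escalate at any point.
- Escalation needs an SRC recommendation, which under 16.2 also weighs other clinical factors.

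All of this stands, and the event is still graded and enters the AE rate. None of it restores the event to the DLT count.

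Fourth, counting does not fix the outcome either: after two DLTs the SRC may still continue at the same dose, and the expansion rule is permissive. That is correct. What changes is the starting point the rule gives the SRC.

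Finally, a main-cause test is a reasonable guard against disease-related edema blocking escalation in cohorts of three to six. That purpose is sound, and it does not require the exemption to reach events already severe enough to meet a local-reaction criterion. The separate SRC charter and DLT form instructions, which are not available here, might address the point, but the definition belongs in the protocol.

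**Conclusion.** The concern holds. As written, the Note can remove from the DLT count an edema at the injected site that is operative, life-threatening or fatal and is attributed to study drug, whenever another cause is judged the main one. The class is narrow, and it vanishes if a site equates attribution with main cause. Where it exists, one event is enough to turn 1/3 into 0/3, 2/6 into 1/6 or 10/30 into 9/30, and each change crosses a decision boundary. The pass probabilities (90.6% exempt, against 87.1%, 81.4% or 70.9% counted) depend entirely on assumed event rates and on applying Table 5 mechanically. They show direction and possible size only. A pass permits escalation without compelling it, and the safeguards reduce the risk to subjects. The DLT component of the primary endpoint and the basis for the recommended Phase II dose would nevertheless be understated. The correction should be made; confidence is moderate because the text admits more than one reading.

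**What to change.** Add one sentence to the Note in Protocol 7.4 and to its copies in the synopsis, Protocol 7.6 and SAP 4.3:

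> *The main-contributory-factor exemption does not apply to an event that satisfies either local-reaction DLT criterion (the operative criterion, or the life-threatening or fatal criterion).*

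Leave the attribution wording of those criteria and the 7.10 triggers as they are. Keep the exemption for all other edema, seizures, headaches and fatigue.

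The cost is one sentence in four places, three in a protocol amendment and one in the SAP, with no new data or visits. The downside is that a few severe edema events confounded by disease may count as DLTs and slow escalation. SAP Table 2 shows Cohort 3 enrolling and Cohort 4 still to come, so at that stage the change could still govern both escalation and any expansion.

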7.5. Recommended Phase II Pediatric Veledimex Dose and Corticosteroid Exposure

The recommended Phase II pediatric veledimex dose will be determined using the Evaluable Safety Population (ESP). The recommended pediatric Phase II dose is defined as the dose level below the dose in which $\geq 33\%$ of subjects in the same cohort experience DLTs. If 2 DLTs occur in the same cohort, dose escalation will stop in the cohort experiencing the DLTs. A decision to enroll additional subjects in an expansion cohort will be made by the SRC.

The recommended pediatric Phase II dose in this study will be determined in the context of variable corticosteroid exposure and will be reported as such. Investigational treatment requires that steroid use be allowed to manage brain tumor related symptoms or edema, especially after tumor resection. It is expected that the use and dose of corticosteroids will vary among trial sites and among subjects, and therefore, the extent and dose of steroids is not specified in this protocol. The treating physician should consider the minimum starting steroid dose for study subjects, if determined that it is safe and appropriate for that individual subject. For study subjects who require a higher starting steroid dose, efforts should be made to taper steroids to the lowest amount that controls the subjects' symptoms, as determined to be safe and appropriate by the treating physician.

7.6. Dose Modification and Dose Delays

Treatment dose delays and dose reductions for individual subjects will be allowed in the event of toxicities, according to the criteria shown in [Table 6](#). If a drug-related Grade 3 or higher AE occurs (excluding nausea and/or vomiting in subjects who did not receive optimal treatment with anti-emetics), the Investigator in conjunction with the Sponsor's Medical Monitor will decide whether the subject will remain on the study. The withheld doses will not be made up; the subject may be allowed to complete dosing according to the remaining schedule.

As mentioned in [Section 7.4](#), fatigue, seizures, headaches, and cerebral or pontine edema are commonly observed in this population and will be recorded according to grade of toxicity, but

will not be considered a DLT unless a relationship to study drug is deemed to be the main contributory factor. If $\geq 33\%$ of subjects experience DLTs, the SRC will convene to determine the course of action. The Medical Monitor or Investigators may request a meeting of the SRC at other times, as deemed clinically indicated.

Table 6: Criteria for Dose Delay and Dose Reduction

Event	Course of Action
Any local injection reaction that requires operative intervention	Hold study drug and contact the Medical Monitor for instructions on resuming dosing
Any local injection reaction that has life-threatening consequences requiring urgent intervention or results in death	Hold study drug and contact the Medical Monitor for instruction on resuming dosing
Any drug-related Grade 3 or higher AE ^a	Hold study drug and contact the Medical Monitor for instruction on resuming dosing

^a Excluding nausea and/or vomiting in subjects who did not receive optimal treatment with anti-emetics

7.7. Safety Monitoring and Adverse Effect Management

Safety will be evaluated in the Overall Safety Population (OSP) and the Evaluable Safety Population (ESP) using National Cancer Institute (NCI) Common Terminology Criteria for Adverse Events (CTCAE) v5.0. Safety assessments will be based on medical review of adverse event reports and the results of vital signs, physical and neurologic examinations, electrocardiograms (ECGs), clinical laboratory tests, and monitoring of the frequency and severity of adverse events. In addition, urine, fecal, saliva, buccal, and blood samples will be collected and tested for viral replication.

7.8. Severity Grading and Management of Local Reactions

Injection of agents into tissue carries a potential risk of local reactions that may be characterized as intense immunologic reaction at or near the injection site. Local reactions will be graded according to the NCI CTCAE v5.0 criteria. Study stopping rules will not apply to a specific event if it is clearly unrelated to study drug administration.

7.9. Prophylactic Antipyretic and/or Analgesic Administration

The use of antipyretics and/or analgesics is allowed as a prophylactic measure perioperatively. Antipyretics and/or analgesics can be used anytime during study treatment, as indicated and required for subject safety and must be recorded as concomitant medications. Please refer to exclusion criteria for acute clinically significant and/or chronic infections.

Note: Because flu-like symptoms (e.g., fever, headache, chills, dehydration, etc.) are commonly experienced following adenoviral vector administration, it is strongly recommended that subjects be treated with prophylactic antipyretic and/or analgesic medication prior to Ad-RTS-hIL-12 injection and during the first week after injection.

Please refer to [Appendix 5](#) for the recommended regimen for the prophylactic administration of antipyretics and/or analgesics.

7.10. Study Stopping Rules

In the DLT evaluation period (Day 0 to Day 28), if any subject experiences a local reaction that requires operative intervention and is felt to be attributable to study drug; any local reaction that has life-threatening consequences requiring urgent intervention or results in death and is felt to be attributable to study drug; or any Grade 4 hematologic toxicity, except thrombocytopenia, that is at least possibly related to study drug and lasts \geq 5 days, enrollment of new subjects will be paused pending review by the SRC.

In the event that there are other subjects actively being dosed in the cohort, the treating site's Principal Investigator (PI) and the Medical Monitor will discuss the relationship to study drug and determine whether or not to convene an urgent SRC meeting to make a decision to continue active dosing in ongoing subjects.

The SRC will make a decision to the enrollment of additional subjects at the relevant veledimex dose level, to expand the current dose level cohort, to de-escalate veledimex dosing at the relevant dose level, or to amend the protocol prior to enrollment of additional subjects, or to discontinue enrollment in the study. In the event that a decision is made to de-escalate dosing, the SRC will evaluate the appropriateness of dosing at a previously evaluated lower dose or exploring an intermediate dose level.

For any subject death within 30 days of study therapy, enrollment will be held pending review of the event by the SRC. Active dosing in ongoing subjects will continue at the discretion of the treating site's PI and the Medical Monitor pending the SRC review.

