7.2. Study Oversight for Safety Evaluation

The first level of safety oversight will occur through the site Investigator in conjunction with the Medical Monitor. The site Investigator will communicate with the Medical Monitor during the active dosing period for all subjects on a daily basis regarding clinical status and laboratory values, prior to the patient receiving their daily dose of veledimex, and additionally as clinically indicated.

A formal Safety Review Committee (SRC), comprised of the study Investigators, the Medical Monitor, and other appropriate Sponsor representatives, will provide the overall safety oversight. Additional external medical and scientific experts may also be invited to participate in the reviews, as needed. A separate charter will outline the SRC activities. Briefly, the SRC will evaluate subject safety within each cohort. If no significant safety events occur with the first subject of each cohort, the second and third subjects will be enrolled and treated. If a significant safety event occurs with the first subject, the SRC will convene to evaluate the safety event(s) and to make a recommendation and decision on the enrollment of the second and third subjects in the same cohort.

Upon completion of each cohort, the SRC will meet to review the data collected to determine next steps as described in Section 7.3. Enrollment in Cohort 4, with the 20 mg assigned

veledimex dose will not commence until the SRC has determined that dosing at the lower level, Cohort 3, did not result in DLTs that would preclude dose escalation.

In addition to recommending the opening of Arm 2 Cohort 3, or dose escalation to Cohort 4, the SRC may also determine if the study should proceed with the Phase II portion (an expansion of an Arm 2 cohort). In the event that the SRC determines that escalation and/or expansion is not warranted, a decision will be made about stopping the investigation. At the discretion of the SRC, the investigation may be continued at a lower dose.

Dose escalation, cohort expansion, and de-escalation rules will be followed as defined in Section 7.3 and study stopping rules will be followed as defined in Section 7.10.

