7.3. Dose Escalation, Cohort Expansion, and De-Escalation Decision Rules

Expansion cohort(s) are prospectively planned in this study, in Arm 2, at the discretion of the SRC.

Each subject in each dose escalation cohort (3+3 standard design) will be monitored for 28 days before subsequent subjects are enrolled. The SRC will convene after the third and/or final subject in each cohort completes the 28-day DLT evaluation period and will make a recommendation regarding expanding the current cohort by up to 30 additional subjects (phase II component), opening of the next cohort/dose escalating, dose de-escalating, or discontinuing the investigation.

If the SRC recommends expanding the current cohort, a 28-day review period may not be required between each patient. Based on the safety profile of the current cohort, the SRC will make a determination related to the waiting period.

The SRC will determine if/when the MTD is met and may recommend cohort expansion at that dose.

Study stopping rules will be followed as defined in [Section 7.10](#).

Dose Escalation/Cohort Expansion

Each subject in each dose escalation cohort (3+3 standard design) will be monitored for 28 days before subsequent subjects are enrolled. The SRC will convene after the final subject in Cohort 1 completes the 28-day DLT evaluation period. The SRC will make a recommendation regarding:

- Opening enrollment of Cohort 3
- Discontinuing the investigation

If the SRC recommends opening enrollment in Cohort 3, each subject will be monitored for 28 days before subsequent subjects are enrolled in the same cohort. The SRC will convene once the third and/or final subjects (*i.e.*.. subject 3 of 3 or 6 of 6) in Cohort 3 complete the 28-day DLT evaluation period. The SRC will make a recommendation regarding:

- Expansion of Cohort 3 (Phase II portion)
- Opening enrollment of Cohort 4
- Discontinuing the investigation

If the SRC recommends enrollment of Cohort 4, each subject will be monitored for 28 days before subsequent subjects are enrolled in the same cohort. The SRC will convene once the third and/or final subject (*i.e.*, subject 3 of 3 or 6 of 6) in Cohort 4 complete the 28-day DLT evaluation period. The SRC will make a recommendation regarding:

- Expansion of Cohort 4 (Phase II portion)
- Discontinuing the investigation

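### Protocol 7.10 has no automatic enrollment pause for a non-fatal life-threatening or operative event due solely to the Day 0 biopsy or injection procedure: a narrow gap that matters mainly in the expansion

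*Protocol*

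**What the plan says.** Protocol 7.10 sets four automatic enrollment pauses. Three apply from Day 0 to Day 28:

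- A local reaction that needs an operation: "if any subject experiences a local reaction that requires operative intervention and is felt to be attributable to study drug".
- A life-threatening or fatal local reaction, again only if attributed to study drug.
- A Grade 4 hematologic toxicity other than thrombocytopenia, at least possibly related to study drug and lasting 5 days or more.

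The fourth has no attribution condition: "For any subject death within 30 days of study therapy, enrollment will be held pending review of the event by the SRC".

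Protocol 7.8 then narrows these rules: "Study stopping rules will not apply to a specific event if it is clearly unrelated to study drug administration".

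Protocol 7.2 requires the SRC to convene after a significant safety event in the first subject of a cohort, whatever the cause, and adds: "A separate charter will outline the SRC activities". That charter is not among the documents.

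In dose escalation, each subject is observed for 28 days before the next is enrolled. For the expansion, Protocol 7.3 relaxes this: "If the SRC recommends expanding the current cohort, a 28-day review period may not be required between each patient". It continues: "Based on the safety profile of the current cohort, the SRC will make a determination related to the waiting period".

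In Arm 2 the Day 0 session includes a stereotactic biopsy before the vector is injected (Protocol 7.1). Protocol 10.1 names intracranial bleeding among procedure-related events and asks for evaluation before that child's first veledimex dose after the injection. Protocol 14.5 assesses relation to a protocol procedure separately from relation to study drug.

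**The concern.** The procedure is part of the trial, its target in Arm 2 is the pons, and the protocol expects that it can cause harm. Yet the rule that protects the next child responds to non-fatal harm only when that harm is ascribed to the drug. In dose escalation the 28-day wait already limits how fast a procedural problem could reach further children, although it is a delay and not a review. In the expansion that wait may be gone. If a child then has a serious non-fatal injury that is judged purely surgical, the written rule lets the next child undergo the same procedure before the SRC has looked at the first case, unless someone chooses to stop.

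**Working it through.** **Step 1: test the event against each rule.** Take a non-fatal hemorrhage on Day 0 that needs surgery or is life-threatening, judged due solely to the biopsy or needle pass, in a subject after the cohort's first.

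- 7.10, operative local reaction: not met, because it is not attributed to study drug.
- 7.10, life-threatening local reaction: not met, for the same reason.
- 7.10, hematologic toxicity: not applicable.
- 7.10, death: not met.
- 7.8: this clause only removes events from the stopping rules. Even if the injection counts as drug administration, the clause creates no trigger.
- 7.2 first-subject review: not applicable. The protocol treats the expansion as an enlargement of an existing cohort. On the SAP's description of a new cohort, this review would cover at most its first child.
- 7.4 expansion rule (at least 33% of subjects with DLTs): the qualifying criteria need attribution or a possible relation to study drug, so this event adds nothing. At full enrollment the rule needs 0.33 × 30 = 9.9, so 10 of 30 children (0.33 × 35 = 11.55, so 12 of 35). Its remedy is a lower veledimex dose, which would not address a surgical cause.
- 7.6, Table 6: has no attribution condition for operative or life-threatening local injection reactions, but holds only the affected child's drug.

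None of these pauses enrollment automatically.

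**Step 2: does the stagger close the gap in the expansion?** Inputs: up to 30 children (Protocol 7.3) or 30 to 35 (SAP 2.2.3); a 28-day interval (Protocol 7.3); 12 months of Phase II accrual (SAP 2.2.3).

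- First to last enrollment under a full stagger is (N − 1) × 28 days. For 30 children: 29 × 28 = 812 days (26.7 months). For 35: 34 × 28 = 952 days (31.3 months).
- The most children that fit in 365 days is 1 + floor(365/28) = 1 + 13 = 14.
- Mean spacing needed for 12 months: 365/29 = 12.6 days for 30, or 365/34 = 10.7 days for 35.
- Children per 28 days at that pace: 30/365 × 28 = 2.3, or 35/365 × 28 = 2.7.

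The 12-month projection is therefore achievable only with a shortened or absent stagger. Protocol 17.4 allows 24 months for enrollment in the whole study, which is also below 26.7 months.

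**Step 3: how often might an added pause be triggered?** The documents give no rate of procedural injury, so this is an illustration over an assumed range. The chance of at least one event among 30 children is 1 − (1 − p)^30: 26.0% at p = 1%, 45.5% at 2%, 78.5% at 5% and 95.8% at 10%.

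**The case against.** The strongest reply is that little is left uncovered and that people are already watching. Biopsy and injection happen in one stereotactic session, so ascribing a bleed wholly to the procedure may be hard; an event with a plausible drug contribution can be rated possibly related. The Investigator and Medical Monitor are in daily contact from Day 0 to Day 14, and the Medical Monitor must agree that each new child is eligible. SAEs go to the sponsor within 24 hours, either party may ask for an SRC meeting, and the study rationale promises ongoing safety review. The expansion is optional. The waiting period is set on the safety profile of the current cohort, and nothing bars the SRC from revisiting it as expansion data accrue. The unseen charter may already contain the pause.

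All of this stands as a limit on the size of the gap. None of it makes review mandatory before the next procedure, as the protocol is written. The biopsy, done before any vector is given in Arm 2, is the clearest case that stays uncovered.

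A second reply concerns cost. Arm 2 children must be 2 to 10 weeks past radiotherapy, a window of 8 weeks, so a long pause could make a waiting child ineligible. If procedural events are not rare, a pause becomes likely. This is a fair point about how the fix should work. The same probabilities also show how often a next child might otherwise proceed without a required review.

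**Conclusion.** The gap is real on the text and narrow. It covers non-fatal life-threatening or operative events judged due solely to the Day 0 procedure, in any subject after a cohort's first. Its practical weight falls on the expansion: up to 30 children (30 to 35 in the SAP), at about 2.3 to 2.7 per 28 days if the 12-month projection is kept. That figure assumes even accrual, and the projection is a planning assumption, not a decision to waive the stagger. No risk of injury can be estimated from the documents. This is a matter of trial conduct and child safety; it does not make any planned analysis wrong.

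Three stronger readings are not supported:

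- A reader might infer that a mechanical bleed falls outside the term local reaction, because 7.8 speaks of "a potential risk of local reactions that may be characterized as intense immunologic reaction at or near the injection site". That wording is not exclusive, and SAP Appendix 1, footnote p, groups hemiparesis and seizure with local reactions. The gap rests on the attribution condition alone.
- A reader might infer that the trial could not stop after a procedural injury. It could, at the discretion of the Investigator, Medical Monitor or SRC. What is missing is the automatic step.
- A reader might infer that these events would vanish from the safety report. SAP 13.1 lists AEs and serious AEs for all treated subjects without an attribution condition.

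**What to change.** Add to Protocol 7.10: a life-threatening event, or one requiring operative intervention, that is attributed to the Day 0 biopsy or injection procedure pauses new enrollment pending prompt SRC review. State that it is not counted as a veledimex DLT and that the 7.8 exemption does not apply to it. If the SRC charter already provides for this, cite it in 7.10 instead.

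The cost is one or two sentences and the time of an existing committee. The downside is a possible short pause for a surgical event. Because of the 2-to-10-week window after radiotherapy, the text should ask for quick review, so that waiting Arm 2 children do not lose eligibility. In dose escalation the added delay is small, because the 28-day wait already applies.
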